# 5.3.4 End of Study Visit

End of study for patients receiving mTOR inhibitor therapy will be within 4 weeks after the last dose of the mTOR inhibitor that they received. End of study for patients receiving radiation to the esophagus will be 6 months (+/- 21 days) after the last day of radiation. The following procedures will be completed at this time:

- Examination of oral mucosa and grading of oral mucositis for patients who received mTOR inhibitor therapy. For patients who received radiation to the esophagus signs and symptoms of esophagitis are to be evaluated.
- Weight
- Concomitant Medications
- ALC may be obtained. Attempts to perform ALC labs will be made at this timepoint, but if unsuccessful, will not be considered a deviation to the protocol since it is not a safety assessment.
- Quality of life questionnaires: MDASI-HN

# 6.0 Study Calendar

- Baseline evaluations are to be conducted within 28 days prior to start of protocol therapy.
- Study Assessments will take place as per protocol schedule unless patient/logistical/medical reasons intervene.

### 6.1 Study Assessment for Patients Receiving mTOR Inhibitor Therapy

All evaluations will have a +/- 2 day window. Cycle 1 Day 1 of the study drug will be Day 1 of the mTOR treatment.

| Study
Assessment                                 | Screening   | Cycle 1  |          |           | Cycle
2 and
Beyond | End of
Study h | 3 months
Post
EOT h
(+/- 14
days) f | 6 months
Post EOT h
(+/- 21
days) f |   |
|---|---|----------|----------|-----------|--------------------------|------------------------------|---|--|---|
|   | Within 28
Days of
Cycle 1
Day 1 (+1
Day Prior
to Dosing) | Day
1 | Day
8 | Day
15 | Day
22                | Day 1                        |   |  |   |
| Informed
Consent                                 | x   |          |          |           |                          |                              |   |  |   |
| Medical
History
Review                        | x   |          |          |           |                          |                              |   |  |   |
| Mucositis
History                                | x   |          |          |           |                          |                              |   |  |   |
| Oral Mucosa
Exam a                    | x   | x        | X        | x         | X                        | X i.              | X i.  |  |   |
| Mucositis
Gradingª                               | x   | x        | x        | x         | x                        | X i.       | X i.  |  |   |
| Weight &
Weight Loss b                | x   | x        | X        | x         | x                        | X                            | X   |  | x |
| Concomitant
Medications                          | x   | x        | X        | x         | x                        | x                            | X   |  |   |
| ALC g                                    | X   |          |          |           |                          | Х                            | Х   |  |   |
| Pregnancy
Test                                   | x   |          |          |           |                          |                              |   |  |   |
| Quality of Life
Questionnaire
c               | x   |          |          | x         |                          | x                            | X   | x  | x |
| Patient
Satisfaction
with Study
Medication |   |          |          |           |                          | x                            |   |  |   |
| Medical
Photography e                 | х   |          |          |           |                          | X                            |   |  |   |

a Mucositis grading according to CTCAE v4.03 to be documented with the oral mucosa exam for patients receiving mTOR inhibitor therapy.

b Weight loss to be calculated at each study assessment visit.

c QOL questionnaires will be performed at 3 months and 6 months if patients are still on mTOR inhibitor-based regimen

d To be done only on Cycle 1 day 29 (prior to receiving Cycle 2 Day 1)

e Medical Photography of the patient's oral mucosa at screening, worst grade of mucositis experienced, and cycle 1 day 29 (prior to beginning cycle 2). Attempts to obtain photographs will be made at these timepoints, but if unsuccessful, will not be considered deviations to the protocol since these are not safety assessments.

fThis visit is for patients who remain on mTOR inhibitor containing therapy up to 3 or 6 months. g. The ALC may be obtained. Attempts to perform ALC labs will be made at these timepoints, but if unsuccessful, will not be considered deviations to the protocol since these are not safety assessments.

h. The End of Study visit will be within 4 weeks after last dose of mTOR inhibitor therapy. The 3-month and 6-month follow-up visit will occur post end of treatment (EOT).

 After 4 weeks of therapy, mucositis symptoms, weight (weight loss), concomitant medications, and questionnaires may be assessed by phone call to the patient.

The investigators are aware that the combination of mTOR inhibitors and glutamine, including sucrose and trehalose, may further increase mTOR inhibitor-induced hyperglycemia. The investigators will work closely with the endocrine collaborator.

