# 3.1 Preparation:

The drug and placebo will be provided by Healios Oncology Nutrition.

**Glutamine (Active):** supplied as a powder. 1 scoop provides the individual serving of 4 grams glutamine (other components include 5 grams (gms) sucrose, 1.3 gm trehalose, 130 mg suspending agent to prevent quick settling, and 0.7 gm flavoring). One scoop is suspended with 25-100 milliliters (mL) water.

**Glycine (Placebo):** supplied as a powder. 1 scoop provides the individual serving of 4 grams glycine (other components include 5 grams (gms) sucrose, 1.3 gm trehalose, 130 mg suspending agent to prevent quick settling, and 0.7 gm flavoring). One scoop is suspended with 25-100 milliliters (mL) water

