# 5.3.3 Evaluation during Study:

- Examination of oral mucosa and grading of oral mucositis weekly during cycle 1 and monthly in subsequent cycles for patients receiving mTOR inhibitor therapy. For patients receiving radiation to the esophagus signs and symptoms of esophagitis (ie: dysphagia, weight loss) are to be evaluated in the routine monitoring weekly visits during therapy, as per the study calendar below.
- Weights to be obtained weekly during cycle 1 and monthly in subsequent cycles for patients receiving mTOR inhibitor therapy. For patients receiving radiation to the esophagus weights are to be obtained weekly during XRT.
- Concomitant medications to be reviewed weekly during cycle 1 and monthly in subsequent cycles for patients receiving mTOR inhibitor therapy and weekly, 4

weeks post last radiation and at 6 months post last radiation for patients receiving radiation to the esophagus .

- Quality of life questionnaire. MDASI-HN for patients receiving mTOR inhibitor therapy on day 15 and day 1 of Cycle 2 and beyond, end of study visit, and 3 months (+/-14 days) and 6 months (+/-21 days) post end of mTOR inhibitor-based therapy. Patients receiving radiation to the esophagus should complete the questionnaires at the Week 3, Week 5 and Week 7, end of treatment (or final week of radiation treatment based on number of weeks of radiation), as well as 1 month (+/-7 days) and 3 months (+/-14 days), and 6 months (+/-21 days) after treatment.
- Patient Satisfaction Survey will be given on Day 1 of Cycle 2 and beyond for patients receiving mTOR inhibitor therapy and given at Week 3,Week 5, Week 7, end of treatment (or final week of radiation treatment based on number of weeks of radiation), and 1 month post treatment for patients receiving radiation to the esophagus.
- For patients on mTOR inhibitor-based therapy, ALC may be obtained at screening and Day 1 of Cycles 2 and beyond. Attempts to perform ALC labs will be made at this timepoint, but if unsuccessful, will not be considered a deviation to the protocol since it is not a safety assessment.
- For patients on radiation therapy, ALC may be weekly during radiation. Attempts to perform ALC labs will be made at these timepoints, but if unsuccessful, will not be considered deviations to the protocol since these are not safety assessments.

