# 10.1 Serious Adverse Event (SAE) Reporting

### Adverse Event Definition

The CTEP active version of NCI Toxicity Criteria may be used by the Investigator as a guide in determining the severity of adverse events.

Clinically significant adverse events (AEs) and Serious Adverse Events (SAEs) occurring during the study that are thought to be related to Glutamine or Best Supportive Care should be documented in the medical record.

Toxicities of all grades that are felt to be related to Glutamine or Best Supportive Care, and all grades of mucositis, esophagitis, and weight loss will be documented in the patient electronic medical record. Unless otherwise documented in the electronic medical record as clinically significant and study drug related, all lab abnormalities will be assumed to be related to the patient's other co-morbid conditions, prior therapies, other concomitant therapies/medications, or underlying cancer. In this study, only adverse events related to the study drug, not related to mTOR inhibitor therapy or radiation therapy will be recorded.

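### The protocol names worsened hyperglycemia as a product risk in mTOR patients but plans no glucose capture, and its recording rules are likely to leave non-serious events out of the toxicity comparison

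*Combined protocol and SAP*

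**What the plan says.** Below the mTOR calendar, section 6.1 says: "The investigators are aware that the combination of mTOR inhibitors and glutamine, including sucrose and trehalose, may further increase mTOR inhibitor-induced hyperglycemia". The only response given is: "The investigators will work closely with the endocrine collaborator". No test, data field or report follows from it.

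The pretreatment, on-study and end-of-study lists (5.3.2 to 5.3.4), the 6.1 calendar and the endpoints (12.2) contain no glucose measurement. The only laboratory items for this cohort are a pregnancy test and an optional lymphocyte count: "For patients on mTOR inhibitor-based therapy, ALC may be obtained at screening and Day 1 of Cycles 2 and beyond". A missed count is not a deviation.

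Under Adverse Event Definition in section 10.1, the default is that "all lab abnormalities will be assumed to be related to the patient's other co-morbid conditions, prior therapies, other concomitant therapies/medications, or underlying cancer". The sentence opens with an exception: "Unless otherwise documented in the electronic medical record as clinically significant and study drug related". The same paragraph ends by saying that "only adverse events related to the study drug, not related to mTOR inhibitor therapy or radiation therapy will be recorded". Section 10.2 repeats the related-only limit for the trial database.

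On the placebo, section 3.1 says: "1 scoop provides the individual serving of 4 grams glycine (other components include 5 grams (gms) sucrose, 1.3 gm trehalose". The active scoop has the same sucrose and trehalose, with 4 g glutamine in place of 4 g glycine. Section 5.1 gives one scoop twice daily in both arms. Section 12.4 promises descriptive toxicity statistics by arm.

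**The concern.** Describing the toxicity of glutamine is a stated secondary objective. Hyperglycemia is a risk that the authors foresaw for their own product in this cohort, yet the plan neither measures it nor clearly allows it to be recorded.

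The wording of section 10.1 makes this worse. The foreseen event is an aggravation of an effect that mTOR inhibitors already cause. An investigator who sees a raised glucose, blinded to arm, has an obvious other cause to hand, and the default points the same way. Read literally, a rule that records only events not related to mTOR therapy excludes an aggravated mTOR effect even when the product is suspected of contributing.

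At stake is a toxicity table showing little or no hyperglycemia in either arm, which readers and the DSMB could take as reassurance when the data were not collected.

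**Working it through.** The plan states no figure for hyperglycemia, so there is none to reproduce. The only stated power for this cohort is 94% for mucositis with 50 per arm. It checks out approximately (92.9% by a tie-corrected approximation, 96.0% by simulation) and has no bearing on this point.

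**1. Route of a raised glucose into the trial data**
- Measurement: no scheduled value in 5.3.2 to 5.3.4 or 6.1.
- Attribution: presumed unrelated to study product unless documented as both clinically significant and product-related (10.1).
- Recording: related-only in 10.1, again in 10.2.
- Concomitant drugs: section 5.3.3 has them reviewed, but section 7.0 specifies recording only of those used to treat mucositis. A newly started glucose-lowering drug is not a dependable trace.
- Serious events: section 10.1 sends every SAE to the IND Office regardless of attribution. This route is intact.

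The gap is therefore non-serious hyperglycemia.

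**2. What the placebo allows to be compared**
- Sugars per day, each arm: 2 × (5 + 1.3) = 12.6 g.
- Between-arm difference: 12.6 − 12.6 = 0 g.
- Amino acid per day: 2 × 4 = 8 g glutamine against 8 g glycine.

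A rise caused by the sugars is equal in both arms. In simulation with 50 per arm, a base rate of 20% and a common increment of 10, 20 or 30 points, a two-sided 5% test rejected in 5.0% to 5.8% of runs, about its nominal rate. The glutamine-versus-glycine contrast stays randomized.

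**3. Cost of incomplete recording**

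The documents give no hyperglycemia rates. Assume true rates of 20% (glycine) and 40% (glutamine), 50 per arm, and the same fraction of events recorded in each arm.

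Power = Φ[(d − 1.96 × SE0)/SE1], with SE0 = √(p̄(1 − p̄) × 2/50) and SE1 = √((p1(1 − p1) + p2(1 − p2))/50).

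Full recording: d = 0.20; p̄ = 0.30; SE0 = √0.0084 = 0.0917; SE1 = √0.0080 = 0.0894; power = Φ[(0.20 − 0.1796)/0.0894] = Φ(0.23) = 59%.

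| Share recorded | Recorded rates | Difference | Power |
|---|---|---|---|
| 100% | 20% vs 40% | 20 points | 59% |
| 50% | 10% vs 20% | 10 points | 29% |
| 25% | 5% vs 10% | 5 points | 16% |
| 10% | 2% vs 4% | 2 points | 8% |

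Equal under-recording leaves the ratio at 2 but shrinks the counts and the difference in proportion.

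**4. What full capture would deliver**

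With 50 per arm, 80% power needs a difference of about 20 points at an assumed glycine-arm rate of 5%, 23 at 10%, 26 at 20%, and 28 at 30% or 40%. For 20% vs 40%, 80% power would need 82 per arm.

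**The case against.** The strongest reply is that the plan has more safeguards than the gap suggests. The attribution default has an explicit exception. Section 10.1 also asks for toxicities of all grades felt to be related to glutamine to be documented in the medical record, and section 10.3 makes the investigator or physician designee assign attribution for each event. SAEs are reported whatever their cause. Patients on investigator-initiated mTOR therapy may well have glucose checked under those protocols. Matched sugars serve the blinding described in 12.5 and isolate glutamine, which is what the objective asks about.

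Much of this stands, and it rules out some stronger readings. A reader might infer that the trial cannot detect hyperglycemia at all, or would report none whatever happened. The exception and the SAE route contradict both. A reader might also count the matched sugars as a flaw in the placebo. They remove only the vehicle contrast.

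It does not close the gap. The exception needs someone to have a glucose value and to judge it product-related while blinded, with mTOR therapy as a ready explanation. It also does not clearly cover an event related to both. The SAE route misses lower grades and changes in glucose. If the parent protocols measure glucose, these documents neither say so nor bring the values in.

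**Conclusion.** The concern holds in a limited form. A named product risk has no planned measurement, and the recording rules are likely to leave non-serious hyperglycemia out of the by-arm table, biasing that table toward showing none. How much is lost cannot be computed from the documents. The 20% and 40% rates and the shares recorded in the working are assumptions, and they take the arms to be under-recorded equally and the table to be built from the trial database.

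Two limits remain after any fix. The sugar contribution is not estimable: the arms do not differ in it, and the product starts on Day 1 of mTOR therapy. A reader might infer that a pooled change from baseline would show the sugar effect, but that change would mix it with the mTOR effect. The glutamine contrast would also be imprecise, at about 59% power in the 20% vs 40% scenario. The aim is an honest safety description, not a test. This is a worthwhile, inexpensive correction and does not touch the primary analysis.

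**What to change.** - Add a glucose row to the 6.1 calendar at screening and Day 1 of each cycle, filled from chemistry already drawn for the patient's mTOR therapy or from blood already taken for the lymphocyte count.
- Exempt hyperglycemia from the attribution default in 10.1 and from the related-only limits in 10.1 and 10.2, so that values and CTCAE grades are recorded regardless of attribution.
- In 12.4, report worst grade and change from baseline by arm, descriptively, with the number of patients who have values. Include the table in DSMB reviews.
- State that the effect of the sucrose and trehalose cannot be separated, and do not present a pooled change as that effect.

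The cost is one calendar row, an exemption sentence in each of 10.1 and 10.2, one table and modest data entry. Values will be incomplete where no blood is drawn: the lymphocyte count is optional, it is not scheduled on Cycle 1 Day 1, and several later assessments may be done by phone. Clinical handling of a high value stays with the investigators.

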### 6.2 Study Assessment for Patients Receiving Radiation to the Esophagus

| Study
Assessment                                 | Screening   | Weeks of Radiation d |   |   |   |   | ond |   | End of
Radiation
Treatment e
Post Radiation
Therapy |  |  | End of
Study                            |
|---|---|---------------------------------|---|---|---|---|-----|---|--|--|--|--|
|   | Within 28
Days of
Day 1 of
Protocol
Therapy | 1                               | 2 | 3 | 4 | 5 | 6   | 7 |  | 1 month
(+/- 7
days) f. | 3 Months
(+/- 14
days) f. | 6 Months
(+/- 21
days) f. |
| Informed
Consent                                 | x   |                                 |   |   |   |   |     |   |  |  |  |  |
| Medical
History Review                           | x   |                                 |   |   |   |   |     |   |  |  |  |  |
| Esophagitis
History a                 | x   |                                 |   |   |   |   |     |   |  |  |  |  |
| Esophagitis
Grade a                   | x   | x                               | x | x | x | х | x   | x |  | х  |  | x  |
| ALC b                                    | x   | x                               | x | х | x | х | x   | x |  | х  |  | ХÞ   |
| Weight &
Weight Loss c                | x   | x                               | x | Х | x | х | Х   | x |  | х  |  | X  |
| Concomitant
Medications                          | x   | x                               | x | х | x | х | x   | x |  | х  |  | X  |
| Pregnancy
Test                                   | x   |                                 |   |   |   |   |     |   |  |  |  |  |
| Quality of Life
Questionnaire                    | x   |                                 |   | x |   | X |     | x | x  | х  | x  | X  |
| Patient
Satisfaction
with Study
Medication |   |                                 |   | x |   | x |     | x | x  | x  |  |  |

All evaluations will have a +/- 2 day window.

a Esophagitis grading will be according to CTCAE v4.03.

b. The ALC may be obtained. Attempts to perform ALC labs will be made at these timepoints, but if unsuccessful, will not be considered deviations to the protocol since these are not safety assessments. If the patient does not return to clinic at 6 month post treatment visit, ALC can be done at the first visit after 6 month post radiation treatment.

c Weight loss to be calculated at each study assessment visit.

d. Number of weeks is based on number of weeks of therapy that patient receives as determined by the treating physician. Radiation will be given daily (Monday through Friday) for 5 days per week.

e. End of Treatment visit will occur at the appropriate timepoint based on the number of weeks of radiation therapy that the patient receives as determined by the physician.

f. For the 1-month, 3-month, and/or 6-month visits, the assessments of esophagitis grading, weight (weight loss), concomitant medications, and questionnaires may be assessed by phone call to the patient if patient is not returning to clinic.

# 7.0 Concomitant medications

Concomitant medications that are being used to treat mucositis will be recorded at each visit.

### 8.0 Criteria for Removal from the Study

Patients may be removed from the study for the following reasons:

- 1. Patient withdraws consent for continued participation or refuses further treatment with the study medication.
- 2. If the patient develops grade 4 mucositis.
- 3. Completion of study medication: 4 weeks post the last dose of the mTOR inhibitor (or after completion of 6 Cycles) or post 6 months after completion of radiation.

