# 12.2 Study Endpoints

# **Primary Endpoints**

• For mTOR inhibitor patients, the severity of oral mucositis will be taken as the maximum grade observed during the 6-month study period. For esophagus radiation patients, the severity of esophagitis will be taken as the highest grade observed by week six.

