### 12.4 Statistical Analysis Plan

Note: Analyses will be performed separately for patients treated with mTOR inhibitors and patients with esophagus radiation.

For the primary objective, we will use the Wilcoxon rank sum test to compare the ordered categories of mucositis/esophagitis severity between treatment arms. A patient must complete at least 60% of the planned doses of placebo or glutamine to be considered evaluable in the statistical analysis. As a sensitivity analysis for the appropriateness of 60% dosing cut-off, we will analyze the outcome according to the proportion of drug taken. The proportional of drug taken will be computed as the ratio of number of doses taken to the total number of doses prescribed. For the mTOR inhibitor group, the denominator will reflect the total time that each patient is on the study. For the esophagus radiation group, the denominator will reflect the total number of doses that are prescribed during the delivery of radiation.

For the secondary objectives/endpoints, we will compare between treatment arms (1) the trajectories of the mucositis/esophagitis scores over time using linear mixed effects; (2) the proportion of patients developing mucositis/esophagitis using a Pearson chi-squared test; (3) the proportion of patients developing grade 3 or higher mucositis/esophagitis using a Pearson chi-squared test; (4) the duration of mucositis/esophagitis using the Wilcoxon rank sum test; (5) the time to develop mucositis/esophagitis using Kaplan-Meier estimates and the log rank test (due to right censoring in patients not developing mucositis/esophagitis); (6) the proportion of patients having treatment interruptions using a Pearson chi-squared test; (7) the

weight change using the Wilcoxon rank sum test; and (8) the QOL survey scores using the Wilcoxon rank sum test.

For the secondary objective of describing the toxicity profile, descriptive statistics will be provided on the grade and type of toxicity by treatment arm.

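### Section 8.0 lets a patient who refuses study drug be taken off the study with no requirement to keep grading, which can truncate the primary maximum and, in the mTOR cohort, hide early stopping from the 60% dose rule

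*Combined protocol and SAP*

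**What the plan says.** Section 8.0 opens its list with "Patients may be removed from the study for the following reasons". The first reason is "Patient withdraws consent for continued participation or refuses further treatment with the study medication". Withdrawal of consent and refusal of the product thus share one criterion and one consequence. The protocol defines no separate status for a patient who is off study drug but still followed.

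Section 12.2 defines the primary endpoints as maxima. For mTOR patients, "the severity of oral mucositis will be taken as the maximum grade observed during the 6-month study period". For radiation patients, "the severity of esophagitis will be taken as the highest grade observed by week six".

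Section 12.4 sets the analysis set: "A patient must complete at least 60% of the planned doses of placebo or glutamine to be considered evaluable in the statistical analysis". The proportion of drug taken is "computed as the ratio of number of doses taken to the total number of doses prescribed". The denominator differs by cohort. "For the mTOR inhibitor group, the denominator will reflect the total time that each patient is on the study", whereas for radiation it is the doses prescribed while radiation is being delivered. As a sensitivity analysis of the 60% cut-off, "we will analyze the outcome according to the proportion of drug taken". Section 12.4 gives no rule for a primary outcome whose grading stopped early.

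Section 5.3.4 places the mTOR end-of-study visit by reference to the last mTOR inhibitor dose, not the last study-drug dose.

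**The concern.** A maximum over a fixed period is only as complete as the observation behind it. The product is swished or swallowed twice a day (Sections 3.2 and 5.1), so it is plausible, though the documents do not say so, that patients whose mouth or esophagus is getting worse are the ones who refuse it. If such a patient leaves the study on that day, the recorded maximum is the grade reached so far, and a later peak is never seen. No later analysis can recover grades that were not collected, including one of all randomized patients.

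In the mTOR cohort the dose rule does not reliably catch this. If removal ends time on study, it also ends the denominator. A few days of grading can then enter the primary test as a 6-month maximum with a high dose ratio, and the dose-proportion sensitivity analysis inherits both the short outcome and the inflated ratio.

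**Working it through.** **1. Dose ratio, mTOR cohort.** Inputs: two doses a day (Section 5.1), four-week cycles (Section 5.1.1), six cycles (named in Section 8.0; their use as the planned length is an assumption). Planned doses = 6 × 28 × 2 = 336. For a patient who takes every dose and then refuses:

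| Refusal after | Doses taken | Ratio if removed at refusal | Ratio over 24 weeks |
|---|---|---|---|
| 10 days | 20 | 20/20 = 100% | 20/336 = 6% |
| 4 weeks | 56 | 56/56 = 100% | 56/336 = 16.7% |
| 12 weeks | 168 | 168/168 = 100% | 168/336 = 50% |

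Over 24 weeks, 60% is 0.6 × 336 = 201.6 doses, or 201.6/14 = 14.4 weeks of full adherence. With time on study ending at refusal, a stop at any week passes if earlier adherence was at least 60%. The ratio equals adherence before refusal: 90% adherence gives 90%, and 50% gives 50%.

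**2. The plan's own power (Section 12.3).** Two-sided 5% Wilcoxon rank sum test, categories 0-1 / 2 / 3. Let θ = P(placebo grade higher) + ½P(tie). Power ≈ Φ[(θ − ½ − 1.96·s₀)/s₁], where s₀ is the tie-corrected null standard error and s₁ the standard error under the alternative.

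- Radiation, 26/37/37 against 50/38/12, 40 per arm: θ = 0.37×0.50 + 0.37×0.88 + ½(0.26×0.50 + 0.37×0.38 + 0.37×0.12) = 0.668. With s₀ = 0.0609 and s₁ = 0.0562, (0.1681 − 0.1193)/0.0562 = 0.87, power 81%. Stated: 81%. Simulated: 81%.
- mTOR, 69/22/9 against 95/5/0, 50 per arm: θ = 0.22×0.95 + 0.09×1 + ½(0.69×0.95 + 0.22×0.05) = 0.632. With s₀ = 0.0388 and s₁ = 0.0360, (0.1323 − 0.0760)/0.0360 = 1.56, power 94%. Stated: 94%. Simulated: 96%.

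Both stated powers reproduce. Simulated values are used below, so that before and after are on one footing.

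**3. Effect of truncation.** Assumption: a share f of grade 2 and grade 3 patients is recorded one category low. New distribution: category 3 = (1−f)p₃; category 2 = (1−f)p₂ + f·p₃; category 0-1 = p₁ + f·p₂. At f = 20%:

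- Radiation placebo: 33.4 / 37.0 / 29.6; glutamine: 57.6 / 32.8 / 9.6.
- mTOR placebo: 73.4 / 19.4 / 7.2; glutamine: 96.0 / 4.0 / 0.

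| Scenario | Radiation | mTOR |
|---|---|---|
| Power, no truncation | 81% | 96% |
| Power, both arms, f = 10% | 77% | 95% |
| Power, both arms, f = 20% | 73% | 93% |
| Power, placebo arm only, f = 20% | 50% | 89% |
| No true effect, glutamine arm only, f = 20%: two-sided rejection (nominal 5%) | 13% | 8% |

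The rates are assumptions. The last two rows show only that the direction of bias depends on which arm refuses more.

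**4. Reach of the radiation figures.** There the denominator is fixed by the radiation course. For a six-week course (assumption), prescribed doses are 42 × 2 = 84, and 60% is 50.4 doses, about day 25. A patient who refuses earlier is excluded as non-evaluable, not entered with a low grade. The radiation column therefore applies only to refusers who still meet the 60% rule, or to an all-randomized analysis.

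**The case against.** Several points on the other side are sound.

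- **Removal is optional.** A reader might infer that refusing the product automatically ends participation. Section 8.0 says only that patients may be removed. That stands, but discretion without criteria leaves follow-up to case-by-case choice.
- **The schedules follow the cancer therapy.** Sections 5.2 and 5.3.4 key assessments to mTOR therapy or radiation. Radiation patients are already followed to 6 months, although study drug stops 4 weeks after radiation (Section 5.1.2). Section 10.1 has all mucositis and esophagitis grades documented in the medical record. So the gap is narrower than a complete absence of follow-up. Still, none of these provisions requires scheduled grading after removal or says that chart grades would feed the endpoint.
- **The ratio is not always 100%.** A reader might infer that early stoppers always count as fully compliant. That needs both no missed doses and a time on study that ends at refusal. If the patient is kept on study to the end of mTOR therapy, as Section 5.3.4 can be read, missed doses accrue and the ratio falls.
- **Timing.** Section 2.1.1 says mTOR mucositis arises mainly in early cycles, and cycle 1 is graded weekly. Late refusal would often come after the peak. Refusal in the first weeks would not.
- **Bias toward glutamine is not shown.** A reader might take the 13% rejection rate as evidence of it. The documents give no basis for more refusal on glutamine: Section 12.5 describes a placebo identical in look and taste, and Section 3.1 gives the same other ingredients. If soreness drives refusal and glutamine works, placebo patients would refuse more, and the bias would run against glutamine.

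**Conclusion.** The concern holds in a limited form. The plan permits removal from the study for refusing study drug, does not require grading afterwards, and measures mTOR dosing against a period that removal can shorten. Followed as written, it can put a truncated maximum into the primary test with a dose ratio of up to 100%. The same mTOR patient can be evaluable or not depending on whether the investigator removes them.

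The effect of stopping observation early on an individual maximum is certain: it can fall or stay the same, never rise. The effect on the trial is not known, because the documents give no refusal rates by arm. Under the assumed 20% one-category shift in both arms, the power loss is small in the mTOR cohort (96% to 93%) and moderate in radiation (81% to 73%), the latter within the limits set by the 60% rule. The documents do not support calling removal mandatory, calling such patients fully compliant in general, or asserting a bias in favor of glutamine. This is a point that should be fixed because the remedy is cheap and the lost data cannot be recovered. It does not invalidate the design.

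**What to change.** In Section 8.0, separate stopping study drug from leaving the study. A patient who refuses further study drug stays on the existing Section 6.1 or 6.2 schedule for grading, weight and MDASI-HN, by phone where that is already allowed. Only withdrawal of consent to follow-up ends assessment.

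In Section 12.4, state that refusal of study drug does not end the mTOR dose denominator, which should run over the patient's mTOR treatment time within the study period. Under the present 60% rule this will make some early stoppers non-evaluable. Their continued grading is what would let an all-randomized comparison include them. Whether the 60% rule should define the primary analysis set is a separate question.

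Cost: a short amendment to Section 8.0 and a sentence in Section 12.4. No new visit types are needed, since assessments follow the cancer therapy. The downside is a few more assessments or calls to patients who have stopped the product.
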